7.1.1. Liver Chemistry Stopping Criteria

The study drug should be interrupted or discontinued if 1 or more of these conditions occur:

Elevation	Exception
ALT or AST >8x ULN	
ALT or AST >5x ULN for more than 2 weeks	
ALT or AST >3x ULN and either TBL >2x ULN or INR >1.5	In participants with Gilbert's syndrome, doubling of direct bilirubin should be used for drug interruption/ discontinuation decisions rather than TBL >2x ULN
ALT or AST >3x ULN with the appearance of fatigue, nausea, vomiting, right upper quadrant pain or tenderness, fever, rash, and/or eosinophilia (>5%)	
ALP >3x ULN, when the source of increased ALP is the liver	
ALP >2.5x ULN and TBL > 2x ULN	In participants with Gilbert's syndrome, doubling of direct bilirubin should be used for drug interruption/ discontinuation decisions rather than TBL>2x ULN
ALP >2.5x ULN with the appearance of fatigue, nausea, vomiting, right upper quadrant pain or tenderness, fever, rash, and/or eosinophilia (>5%)	

Source: FDA Guidance for Industry: Drug-Induced Liver Injury: Premarketing Clinical Evaluation, July 2009 and other consensus guidelines, with minor modifications

Abbreviations: ALP = alkaline phosphatase; ALT = alanine aminotransferase; AST = aspartate aminotransferase; INR = international normalized ratio; TBL = total bilirubin; ULN= upper limit of normal.

Resumption of the study drug can be considered only in consultation with the Lilly-designated medical monitor and only if the liver test results return to baseline and if a self-limited, non-drug etiology is identified.

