8.2.3. Hepatic Safety Close hepatic monitoring

Laboratory tests (Appendix 10.6), including ALT, AST, ALP, TBL, direct bilirubin (D. Bil), gamma-glutamyltransferase (GGT), and creatine kinase (CK), should be repeated within 48 to 72 hours to confirm the abnormality and to determine if it is increasing or decreasing, if 1 or more of these conditions occur:

If a participant with baseline results of	develops the following elevations:
ALT or AST <1.5x ULN	ALT or AST ≥3x ULN
ALP <1.5x ULN	ALP ≥2x ULN
TBL <1.5x ULN	TBL ≥2x ULN, except for participants with Gilbert's syndrome
ALT or AST ≥1.5x ULN	ALT or AST ≥2x baseline
ALP ≥1.5x ULN	ALP ≥2x baseline
TBL ≥1.5x ULN	TBL ≥1.5x baseline, except for participants with Gilbert's syndrome

If the abnormality persists or worsens, clinical and laboratory monitoring, and evaluation for possible causes of abnormal liver tests should be initiated by the investigator in consultation with the Lilly-designated medical monitor. At a minimum, this evaluation should include physical examination and a thorough medical history, including symptoms, recent illnesses (for example, heart failure, systemic infection, hypotension, or seizures), recent travel, history of concomitant medications (including over the counter), herbal and dietary supplements, history of alcohol drinking and other substance abuse.

Initially, monitoring of symptoms and hepatic biochemical tests should be done at a frequency of 1 to 3 times weekly, based on the participant's clinical condition and hepatic biochemical tests. Subsequently, the frequency of monitoring may be lowered to once every 1 to 2 weeks, if the participant's clinical condition and laboratory results stabilize. Monitoring of ALT, AST, ALP, and TBL should continue until levels normalize or return to approximate baseline levels.

Comprehensive hepatic evaluation

A comprehensive evaluation should be performed to search for possible causes of liver injury if 1 or more of these conditions occur:

If a participant with baseline results of	develops the following elevations:
ALT or AST <1.5x ULN	ALT or AST ≥3x ULN with hepatic signs/symptoms ^a , or ALT or AST ≥5x ULN
ALP <1.5x ULN	ALP ≥3x ULN
TBL <1.5x ULN	TBL ≥2x ULN (except for participants with Gilbert's syndrome)
ALT or AST ≥1.5x ULN	ALT or AST $\ge 2x$ baseline with hepatic signs/symptoms ^a , or ALT or AST $\ge 3x$ baseline
ALP≥1.5x ULN	ALP ≥2x baseline
TBL≥1.5x ULN	TBL ≥2x baseline (except for participants with Gilbert's syndrome)

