^a Hepatic signs or symptoms are severe fatigue, nausea, vomiting, right upper quadrant abdominal pain, fever, rash, and/or eosinophilia >5%.

At a minimum, this evaluation should include physical examination and a thorough medical history, as outlined above, as well as tests for prothrombin time (PT)-INR; tests for viral hepatitis A, B, C, or E; tests for autoimmune hepatitis; and an abdominal imaging study, for example, ultrasound or CT scan.

Based on the participant's history and initial results, further testing should be considered in consultation with the Lilly-designated medical monitor, including tests for hepatitis D virus (HDV), cytomegalovirus (CMV), Epstein-Barr virus (EBV), acetaminophen levels, acetaminophen protein adducts, urine toxicology screen, Wilson's disease, blood alcohol levels, urinary ethyl glucuronide, and blood phosphatidylethanol. Based on the circumstances and the investigator's assessment of the participant's clinical condition, the investigator should consider referring the participant for a hepatologist or gastroenterologist consultation, magnetic resonance cholangiopancreatography, endoscopic retrograde cholangiopancreatography, cardiac echocardiogram, or a liver biopsy.

Additional hepatic data collection (hepatic safety CRF) in study participants who have abnormal liver tests during the study

Additional hepatic safety data collection in hepatic safety CRF should be performed in study participants who meet 1 or more of the following 5 conditions:

- 1. Elevation of serum ALT to ≥5x ULN on 2 or more consecutive blood tests, if baseline ALT <1.5x ULN
 - ➤ In participants with baseline ALT \ge 1.5x ULN, the threshold is ALT \ge 3x baseline on 2 or more consecutive tests
- 2. Elevated TBL to \geq 2x ULN, if baseline TBL <1.5x ULN, except for cases of known Gilbert's syndrome
 - ➤ In participants with baseline TBL \ge 1.5x ULN, the threshold should be TBL \ge 2x baseline
- 3. Elevation of serum ALP to $\ge 2x$ ULN on 2 or more consecutive blood tests, if baseline ALP < 1.5x ULN
 - ➤ In participants with baseline ALP \ge 1.5x ULN, the threshold is ALP \ge 2x baseline on 2 or more consecutive blood tests
- 4. Hepatic event considered to be an SAE
- 5. Discontinuation of study drug due to a hepatic event

Note: the interval between the 2 consecutive blood tests should be at least 2 days.

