Hepatocellular Drug-Induced Liver Injury Screening Plot (TBL vs. ALT or AST)	SS
Hepatocellular Drug-Induced Liver Injury Screening Table	SS
Cholestatic Drug-Induced Liver Injury Screening Plot (TBL vs. ALP)	SS
Cholestatic Drug-Induced Liver Injury Screening Table	SS
Participant profiles will be created for participants meeting criteria for a comprehensive hepatic evaluation (as defined in the protocol). Participant profiles will include demographics, disposition, information collected on the hepatic safety CRFs (where applicable) and a display of study drug exposure, adverse events, medications, blood pressure, heart rate, and the liver -related measurements over time.	SS

Abbreviations: ALP = alkaline phosphatase; ALT = alanine aminotransferase; AST = aspartate aminotransferase; CRF = case report form; DBL = direct bilirubin; INR = international normalized ratio, GGT = gamma-glutamyl transferase; TBL = total bilirubin; ULN = upper limit of normal. Planned and unplanned measurements will be included. The measurements do not need to be taken at the same blood draw. Maximum baseline will be the maximum non-missing observation in the baseline period. The maximum value will be the maximum non-missing value from the postbaseline period.

The primary purpose of the screening plots is to identify participants whose data warrant further review. For these plots, symbols will be used to indicate the randomized treatment.

For individual participants of interest, participant profiles will be reviewed. The review will include which treatment the participant was taking over time, the changes in hepatic labs over time, and the temporal association with potential causes. The review of participant profiles will also include the identification of any potential Hy's law case or potential cholestatic liver injury case that could have been missed by focusing only on the maximum values when determining 30-day time associations.

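### Some participants can meet a liver stopping criterion in Protocol Section 7.1.1 without meeting the Section 8.2.3 criteria that trigger the full hepatic work-up and the SAP's liver profile

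*Protocol*

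**What the plan says.** **Stopping rule (Protocol 7.1.1).** Study drug is to be interrupted or discontinued if any listed condition occurs. Two conditions combine an enzyme limit with symptoms: "ALT or AST >3x ULN with the appearance of fatigue, nausea, vomiting, right upper quadrant pain or tenderness, fever, rash, and/or eosinophilia (>5" percent) and "ALP >2.5x ULN with the appearance of fatigue, nausea, vomiting, right upper quadrant pain or tenderness, fever, rash, and/or eosinophilia (>5" percent). Two combine an enzyme limit with liver function: "ALT or AST >3x ULN and either TBL >2x ULN or INR >1.5" and "ALP >2.5x ULN and TBL > 2x ULN". In Gilbert's syndrome, doubling of direct bilirubin replaces the total bilirubin limit. Restart requires consultation with the medical monitor, liver tests back at baseline, and a self-limited cause other than the drug.

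**Comprehensive evaluation (Protocol 8.2.3).** For baseline values below 1.5x ULN the triggers are "ALT or AST ≥3x ULN with hepatic signs/symptoms" (or 5x ULN and above without symptoms), ALP at or above 3x ULN, and total bilirubin at or above 2x ULN except in Gilbert's syndrome. Footnote a defines the symptoms: "Hepatic signs or symptoms are severe fatigue, nausea, vomiting, right upper quadrant abdominal pain, fever, rash, and/or eosinophilia >5" percent. The minimum content is examination, history, PT-INR, "tests for viral hepatitis A, B, C, or E; tests for autoimmune hepatitis; and an abdominal imaging study, for example, ultrasound or CT scan".

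**Reporting (SAP 4.6.7.1.1, Table EKBC.4.5).** "Participant profiles will be created for participants meeting criteria for a comprehensive hepatic evaluation (as defined in the protocol").

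Neither section of the protocol says that meeting a stopping criterion also triggers the comprehensive evaluation.

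**The concern.** One would expect a liver finding serious enough to halt dosing to lead also to the fixed diagnostic work-up and to an individual display in the report. Here the two rules were written with different symptom lists and different ALP limits, so one does not contain the other. At stake is the completeness of information on participants taken off drug for a possible symptomatic liver reaction. The protocol makes their restart depend on an identified non-drug cause, yet the viral, autoimmune and imaging tests that could identify one are mandatory only under the evaluation that they may not trigger. The SAP's profile rule points to the same evaluation criteria and so inherits the omission.

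**Working it through.** No power or sample-size figure is involved. The check sets the two rules side by side for baseline values below 1.5x ULN and looks for results that meet 7.1.1 but nothing in the comprehensive-evaluation table of 8.2.3.

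| Leg | 7.1.1 (stop or interrupt) | 8.2.3 (comprehensive evaluation) | Gap |
|---|---|---|---|
| ALT/AST with symptoms | >3x ULN; any fatigue; RUQ pain or tenderness | ≥3x ULN; severe fatigue; RUQ abdominal pain | (a) >3x to <5x ULN with only non-severe fatigue or RUQ tenderness |
| ALP with symptoms | >2.5x ULN | none; ALP ≥3x ULN only | (b) >2.5x to <3x ULN with any listed symptom |
| ALT/AST with INR | >3x ULN and INR >1.5 | no INR row | (c) >3x to <5x ULN, INR >1.5, no footnote-a symptom |
| Bilirubin in Gilbert's syndrome | doubled direct bilirubin with ALT/AST >3x or ALP >2.5x ULN | TBL row exempts Gilbert's; no direct-bilirubin row | (d) those stopped on direct bilirubin |
| ALT/AST or ALP with TBL, no Gilbert's | TBL >2x ULN | TBL ≥2x ULN suffices | none |
| ALT/AST >8x, or >5x for more than 2 weeks | stop | ≥5x ULN suffices | none |
| ALP >3x ULN (hepatic source) | stop | ≥3x ULN suffices | none |

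A gap case must also miss every other evaluation trigger. Outside Gilbert's syndrome, (a) to (c) therefore need TBL <2x ULN; (a) and (c) also need ALP <3x ULN, and (b) is stated for ALT/AST <3x ULN. None of the four depends on the rows expressed as multiples of a raised baseline.

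Worked examples, with baselines below 1.5x ULN:
- ALT 3.5x ULN, mild fatigue only, TBL <2x, ALP <3x: 3.5 > 3 with fatigue, so 7.1.1 is met. In 8.2.3, 3.5 < 5 and the fatigue is not severe, so no trigger is met.
- ALP 2.6x ULN, nausea, TBL <2x, ALT/AST <3x: 2.6 > 2.5 with a listed symptom, so 7.1.1 is met. In 8.2.3, 2.6 < 3 and ALP has no symptom leg, so no trigger is met.

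As a check for completeness, the rules were applied to a grid of 8 ALT/AST values, 7 ALP values, 4 TBL values, 2 INR values, 6 symptom states and 3 Gilbert's/direct-bilirubin states: 8 × 7 × 4 × 2 × 6 × 3 = 8,064 combinations. The time-based criterion was left out because 5x ULN already triggers evaluation. Of these combinations, 6,474 meet a stopping criterion and 1,068 of those meet no evaluation criterion. Where only one stopping criterion applied, the gaps fell under (a) to (d). All 1,068 meet a close-monitoring trigger in 8.2.3 (ALT/AST ≥3x or ALP ≥2x ULN). These are counts of grid points and say nothing about frequency in participants.

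**Size in participants.** The documents give no incidence. Purely as an assumption, if 1% to 2% of 233 reached the laboratory bands, that would be 233 × 0.01 = 2.3 to 233 × 0.02 = 4.7, about 2 to 5. Those in a gap are only the subset without another trigger, so this is a ceiling under that assumption, and the number may be zero.

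**The case against.** The strongest reply is that two rules with different purposes may have different thresholds, that each can be applied as written, and that other provisions cover these participants:

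- Every gap case meets close monitoring, with repeat tests in 48 to 72 hours. If the abnormality persists or worsens, an evaluation for causes follows in consultation with the medical monitor.
- Section 8.2.2 asks for the etiology when clinically significant values do not normalise in reasonable time, and Appendix 10.3.4 requires a causality assessment for every adverse event.
- The hepatic safety CRF applies on discontinuation for a hepatic event, on a serious hepatic event, or at ALP ≥2x ULN on two consecutive tests. The last of these would catch most of group (b) once confirmed.
- SAP 4.6.3 gives narratives for permanent discontinuation due to adverse events, and SAP 4.6.7.1.1 provides for review of profiles for participants of interest.

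Much of this stands. A reader might infer that these participants get no search for other causes, or that causality cannot be judged in the most important cases. The documents support neither. A basic search is required if the abnormality persists or worsens, and outside Gilbert's syndrome the gap cases are the milder ones: ALT/AST at or above 5x ULN, or TBL at or above 2x ULN, triggers the full evaluation. Nor can one infer that sites are unable to apply the rules, since each section gives its own list. Some sites may read tenderness as abdominal pain, but the fatigue difference remains.

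What the reply does not remove: the minimum close-monitoring evaluation is examination and history. PT-INR is not in the routine laboratory list of Appendix 10.2 and is not among the close-monitoring tests named in 8.2.3, although INR is part of a stopping criterion. A participant only interrupted at ALT 3.5x ULN with mild fatigue meets no hepatic CRF condition on those findings and gets no narrative unless the event is serious. Review of participants of interest is discretionary, and the screening plots show enzymes and bilirubin, not symptoms.

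**Conclusion.** The mismatch is real and can be read directly from the text. With baseline liver tests below 1.5x ULN, four kinds of participant can meet a stopping criterion without being required to have the comprehensive evaluation and without a guaranteed liver profile. What they lack is the mandatory fixed work-up and the assured individual display; monitoring and a conditional search for causes remain. The number affected may be zero to a few. No efficacy estimate or adverse-event count changes. The point still merits correction because it bears on individual liver safety assessment in a trial of about 233 participants, and because restart depends on a cause that the protocol does not require to be fully sought. The conclusion assumes that each table is applied literally; nothing bars an investigator from doing more.

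**What to change.** 1. **Protocol.** The sponsor's clinicians should reconcile Sections 7.1.1 and 8.2.3 on four items: the symptom list, the ALP limit with symptoms, the INR leg and the Gilbert's syndrome leg. If a difference is intended, the protocol should say so. Which definition or limit is right is for them to decide. The cost is wording in the tables and footnote a.

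2. **SAP Table EKBC.4.5.** Create participant profiles for those who meet the comprehensive-evaluation criteria **or any Section 7.1.1 criterion**. This is one line, changes reporting only and alters no participant's care. It can be made whatever the outcome of item 1, and it costs at most a few extra profiles.

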8.2.4. Hypersensitivity Reactions

Many drugs, including oral agents and biologic agents, carry the risk of systemic hypersensitivity reactions. If such a reaction occurs, additional data should be provided to the sponsor in the designated CRFs.

Sites should have appropriately trained medical staff and appropriate medical equipment available when study participants are receiving study intervention. It is recommended that participants who experience a systemic hypersensitivity reaction be treated per national and international guidelines.

In the case of a suspected systemic hypersensitivity event, additional blood samples should be collected as described in Appendix 10.2.1. Laboratory results are provided to the sponsor via the central laboratory.

8.2.5. Hepatitis B Testing and Monitoring

As specified in the SoA (Section 1.3), initial testing for HBV infection includes HBsAg and hepatitis B core antibody (HBcAb).

- If HBsAg is positive, the participant is excluded.
- If HBsAg is negative and HBcAb is negative, the participant is not excluded.
- If HBsAg is negative and HBcAb is positive, further testing for HBV DNA is required.
 - If the screening HBV DNA is positive, the participant is excluded.

• If the screening HBV DNA is negative, the participant is not excluded. Repeat testing for HBV DNA is required at least every 3 months during the study.

Management of enrolled participants with detectable HBV DNA during the study

If HBV DNA is detected, study intervention will be temporarily withheld or permanently discontinued, as described in Section 7.1, and the participant should receive appropriate follow-up medical care.

8.2.6. Hepatitis C Testing

As specified in the SoA (Section 1.3), initial testing for HCV infection includes testing for anti-HCV.

- If anti-HCV is positive, a test for circulating HCV RNA is required.
- If HCV RNA test is negative, the participant is not excluded.
- If HCV RNA test is positive, the participant is excluded.

Participants who have had HCV infection and have been successfully treated, defined as a sustained virologic response (HCV RNA by PCR negative for at least 24 weeks following treatment completion), are not excluded on the basis of HCV as long as HCV RNA test is negative at screening.

If HCV RNA is detected during the study, the study intervention will be discontinued (Section 7.1), and the participant should receive appropriate follow-up medical care.

8.3. Adverse Events, Serious Adverse Events, and Product Complaints

The definitions of the following events can be found in Appendix 10.3:

- AEs
- SAEs, and
- Product complaints (PCs).

These events will be reported by the participant (or, when appropriate, by a caregiver, surrogate, or the participant's legally authorized representative).

The investigator and any qualified designees are responsible for detecting, documenting, and recording events that meet these definitions and remain responsible for following up events that are serious, considered related to the study intervention or study procedures, or that caused the participant to discontinue the study intervention or study (see Section 7).

Care will be taken not to introduce bias when detecting events. Open-ended and non-leading verbal questioning of the participant is the preferred method to inquire about event occurrences.

After the initial report, the investigator is required to proactively follow each participant at subsequent visits or contacts. All SAEs will be followed until resolution, stabilization, the event is otherwise explained, or the participant is lost to follow-up (as defined in Section 7.3). For PCs, the investigator is responsible for ensuring that follow-up includes any supplemental investigations as indicated to elucidate the nature and/or causality. Further information on follow-up procedures is provided in Appendix 10.3.

8.3.1. Timing and Mechanism for Collecting Events

This table describes the timing, deadlines, and mechanism for collecting events.

Event	Collection	Collection	Timing for Reporting	Mechanism for	Back-up
Event	Start	Stop	to Sponsor or Designee	Reporting	Method of Reporting
Adverse Event					
AE	Signing of the ICF	Participation in study has ended	As soon as possible upon site awareness	AE CRF	N/A
AE – related to prescreening study procedure	Signing of the prescreening ICF	Signing of the ICF	As soon as possible upon site awareness	AE CRF	N/A
Serious Adverse	Event				
SAE and SAE updates – prior to start of study intervention and deemed reasonably possibly related to study procedures	Signing of the ICF	Start of intervention	Within 24 hours of awareness	SAE CRF	SAE paper form
SAE and SAE updates – after start of study intervention	Start of intervention	Participation in study has ended	Within 24 hours of awareness	SAE CRF	SAE paper form
SAE ^a – after participant's study participation has ended and the investigator becomes aware	After participant's study participation has ended	N/A	Promptly	SAE paper form	N/A

Event	Collection Start	Collection Stop	Timing for Reporting to Sponsor or Designee	Mechanism for Reporting	Back-up Method of Reporting
Pregnancy					
Pregnancy in female participants and female partners of male participants	After the start of study intervention	At least 65 days after the last dose of study intervention	Within 24 hours (see Section 8.3.2)	Pregnancy paper form	Pregnancy paper form
Product Complain	ints				
PC associated with an SAE or might have led to an SAE	Start of study intervention	End of study intervention	Within 24 hours of awareness	PC form	N/A
PC not associated with an SAE	Start of study intervention	End of study intervention	Within 1 business day of awareness	PC form	N/A
Updated PC information	_		As soon as possible upon site awareness	Originally completed PC form with all changes signed and dated by the investigator	N/A
PC, if investigator becomes aware	Participation in study has ended	N/A	Promptly	PC form	

Abbreviations: AE = adverse event; CRF = case report form; ICF = informed consent form; N/A = not applicable; PC = product complaint; SAE = serious adverse event.

8.3.2. Pregnancy

Collection of pregnancy information

Male participants with partners who become pregnant

• The investigator will attempt to collect pregnancy information on any male participant's female partner who becomes pregnant while the male participant is in this study. This applies only to male participants who receive study intervention.

^a SAEs should not be reported unless the investigator deems them to be possibly related to study treatment or study participation.

• After learning of a pregnancy in the female partner of a study participant, the investigator will

- obtain a consent to release information from the pregnant female partner directly, and
- o within 24 hours after obtaining this consent will record pregnancy information on the appropriate form and submit it to the sponsor.

The female partner will also be followed to determine the outcome of the pregnancy. Information on the status of the mother and child will be forwarded to the sponsor. Generally, the follow-up will be no longer than 6 to 8 weeks following the estimated delivery date. Any termination of the pregnancy will be reported regardless of gestational age, fetal status (presence or absence of anomalies), or indication for the procedure.

Female participants who become pregnant

- The investigator will collect pregnancy information on any female participant who becomes pregnant while participating in this study. The initial information will be recorded on the appropriate form and submitted to the sponsor within 24 hours of learning of a participant's pregnancy.
- The participant will be followed to determine the outcome of the pregnancy. The investigator will collect follow-up information on the participant and the neonate and the information will be forwarded to the sponsor. Generally, follow-up will not be required for longer than 6 to 8 weeks beyond the estimated delivery date. Any termination of pregnancy will be reported, regardless of gestational age, fetal status (presence or absence of anomalies), or indication for the procedure.
- While pregnancy itself is not considered to be an AE or SAE, any pregnancy complication or elective termination of a pregnancy for medical reasons will be reported as an AE or SAE.
- A spontaneous abortion (occurring at <20 weeks gestational age) or still birth (occurring at ≥20 weeks gestational age) is always considered to be an SAE and will be reported as such.
- Any post-study pregnancy-related SAE considered reasonably related to the study intervention by the investigator will be reported to the sponsor as described in protocol Section 8.3.1. While the investigator is not obligated to actively seek this information in former study participants, he or she may learn of an SAE through spontaneous reporting.
- Any female participant who becomes pregnant while participating in the study will discontinue study intervention or be withdrawn from the study. If the participant is discontinued from the study, follow the standard discontinuation process and continue directly to the follow-up phase. The follow-up on the pregnancy outcome should continue independent of intervention or study discontinuation.

